6. INTERVENTION (IF APPLICABLE)

6.1 Baseline Assessments

After obtaining informed consent and registering the patient in the study the following clinical and baseline assessments will be undertaken:

- A clinical history and review of concomitant medications.
- Specific history related to family history of prostate cancer and urinary symptoms.
- Ethnicity will be recorded.
- Physical examination including digital rectal examination (DRE)
- IPSS, SF-12, CWS and STAI questionnaire

6.2 Laboratory assessments

The participant will undergo venous blood sampling for:

- PSA - collected prior to rectal exam.
- Biobanking of urine/blood
- Episwitch biomarker panel

The specific collection procedures for each these samples are detailed in a Standard Operating Procedure (SOP Serum and Urine Samples).

6.3 BP-MRI and CAD/AI

All men will undergo a screening prostate MRI. It is not necessary for participants to have a renal function performed prior to MRI as the scan is performed without contrast. Specifics of MRI protocol, sequences and reporting employed will be detailed in a Standard Operating Procedure (SOP MRI). An antispasmodic agent such as Hyoscine butylbromide should be administered prior to the scan. If there are contra indication then Glucagon can be administered. The presence of a discrete radiological score 3, 4 or 5 lesion recorded by radiologist or a lesion on CAD/AI leads to a targeted biopsy. All MRIs will be reported by experienced uro-radiologists who are compliant with the standards laid down by the British Society of Uro-Radiology (BSUR).

6.4 Prostate USS

Participants will be offered to undergo an ultrasound prior to MRI. The technique for image acquisition and reporting will be standardised in a Standard Operating Procedure (SOP MP-USS). Participants who have identified prostate lesions on ultrasound scored as 3 or greater by the relevant scoring system will be offered a prostate biopsy.

PROSTAGRAM	Protocol no: 18HH4595	Sponsor: Imperial College London	V 1.01MAY2019
-------------------	---------------------------------	---	----------------------

6.5 Questionnaires

Participants will complete the following validated questionnaires during the study in addition to questionnaires at baseline

1. SF-12

It consists of 36 items to derive eight profiles of functional health and well-being. This will be completed at baseline (T0), following receiving test results (T1) and in those with a positive test requiring a biopsy after the biopsy result (T2)

2. The Spielberger state-trait anxiety inventory (STAI)

This has been widely used to evaluate the impact of the screening process on healthy participants. It is designed to assess the changes in transitory anxiety such as might be experienced in a screening programme.

This will be completed at baseline (T0), following receiving test results (T1) and in those with a positive test requiring a biopsy after the biopsy result (T2)

3. The Cancer Worry Scale (CWS)

The CWS was originally created to assess breast cancer worry and has been adapted for other malignancies including colon and prostate cancer. The revised CWS scale consists of three questions, one question regarding the frequency of cancer worry and two questions regarding the impact of worry about prostate cancer on mood, and daily functioning, respectively.

This will be completed at baseline (T0), following receiving test results (T1) and in those with a positive test requiring a biopsy after the biopsy result (T2)

4. Modified Expected burden questionnaire (EBQ) and perceived burden questionnaire (PBQ)

The EBQ and PBQ evaluate information on the expected embarrassment, pain and burden of a diagnostic test. They have been validated in FOBT and CT colonoscopy screening and modified for this population. The EBQ will be completed prior to each test and the PBQ following each test.

6.6 Prostate biopsy

Men will proceed to biopsy if any screening test is positive. This includes

- PSA: A raised PSA is defined as $PSA \geq 3.0 \text{ ng/ml}$ as per UK screening guidelines
- MRI: The presence of a discrete radiological score 3, 4 or 5 as scored by a radiologist or lesion on CAD/AI
- Ultrasound: The presence of prostate lesions on ultrasound

If there is a lesion detected on an image based screening test men will have image-fusion guided biopsies for each lesion detected under local anaesthetic or sedation. The targeted

PROSTAGRAM	Protocol no: 18HH4595	Sponsor: Imperial College London	V 1.01MAY2019
-------------------	---------------------------------	---	----------------------

biopsy procedure will follow a Standard Operating Procedure (SOP Prostate Biopsies). Men will have been randomised by means of random number generator result to have either their MRI or ultrasound derived lesions biopsies first in order to overcome incorporation bias affecting the biopsy procedure.

If no lesion is identified, men will have a systematic prostate biopsy as per the local centre standard of care pathway. Prostate biopsy tissues samples will be preserved in formalin as soon as they are taken. All biopsy samples will be transported to Imperial College Healthcare NHS Trust for processing. No additional samples will be taken beyond what is required for a clinical diagnosis as outlined in the biopsy SOP.

The prostate biopsy samples will be stored in Imperial College Healthcare NHS Trust pathology department for a period of 30 years of and destroyed as per the standard operating regulations of the NHS laboratories.

The prostate biopsy samples will be stored in Imperial College Healthcare NHS Trust pathology department for a period of 30 years of and destroyed as per the standard operating regulations of the NHS laboratories.

PROSTAGRAM	Protocol no: 18HH4595	Sponsor: Imperial College London	V 1.01MAY2019
-------------------	---------------------------------	---	----------------------

7. SAFETY REPORTING

7.1 Specification of safety parameters

Safety parameters will include the following:

1. Urinalysis: Testing for both nitrite and leukocyte esterase as indicators of bacteriuria
2. Blood tests for PSA: Values outside the reference range will be flagged and the abnormal values will be presented
3. The frequency and incidence of serious adverse events (SAE) occurring through the course of the study

7.2 Adverse Event (AE)

An AE is any untoward medical occurrence in a patient or clinical trial subject. An AE can therefore be any unfavourable and unintended sign (including an abnormal laboratory finding), symptom, whether or not considered related to the trial protocol.

7.3 Adverse Event recording

For the purposes of the study, AEs will be followed up according to local practice until the event has stabilised or resolved, or the Follow-up Visit, whichever is the sooner. Serious adverse Events (SAE) will be recorded throughout the study.

7.4 Severity of Adverse Events

Mild: Awareness of event but easily tolerated

Moderate: Discomfort enough to cause some interference with usual activity

Severe: Inability to carry out usual activity

7.5 Causality of Adverse Events

Unrelated: No evidence of any causal relationship

Unlikely: There is little evidence to suggest there is a causal relationship (e.g. the event did not occur within a reasonable time after a study procedure). There is another reasonable explanation for the event (e.g. the patient's clinical condition, other concomitant treatment).

Possible: There is some evidence to suggest a causal relationship (e.g. because the event occurs within a reasonable time after conducting a study procedure). However, the influence of other factors may have contributed to the event (e.g. the patient's clinical condition, other concomitant treatments).

PROSTAGRAM	Protocol no: 18HH4595	Sponsor: Imperial College London	V 1.01MAY2019
-------------------	---------------------------------	---	----------------------

Probable: There is evidence to suggest a causal relationship and the influence of other factors is unlikely.

Definite: There is clear evidence to suggest a causal relationship and other possible contributing factors can be ruled out.

7.6 Serious Adverse Events

7.6.1 Definition of SAE

An SAE is defined as any event that

- Results in death;
- Is life-threatening*;
- Requires hospitalisation or prolongation of existing inpatient's hospitalisation**;
- Results in persistent or significant disability or incapacity;
- Is a congenital abnormality or birth defect;

* "Life-threatening" in the definition of "serious" refers to an event in which the subject was at risk of death at the time of the event; it does not refer to an event which hypothetically might have caused death if it were more severe.

** "Hospitalisation" means any unexpected admission to a hospital department. It does not usually apply to scheduled admissions that were planned before study inclusion or visits to casualty (without admission).

Medical judgement should be exercised in deciding whether an adverse event/reaction is serious in other situations. Important adverse events/reactions that are not immediately life threatening, or do not result in death or hospitalisation but may jeopardise a subject, or may require intervention to prevent one of the other outcomes listed in the definition above should also be considered serious.

7.7 Expected Study-Related Adverse Events

The following AEs that could be reasonably expected during the course of the study for each procedure.

Expected Adverse Events Associated with Venepuncture Procedure

- Haematomas and ecchymoses around venepuncture site
- Minor discomfort
- Infection

PROSTAGRAM	Protocol no: 18HH4595	Sponsor: Imperial College London	V 1.01MAY2019
-------------------	---------------------------------	---	----------------------

7.8 Expected Adverse Events Associated with MRI

The following Adverse Events are associated with MRI:

- Claustrophobia
- Anxiety/Stress
- Discomfort

Note: No contrast agent is used in the study prostate MRI protocol

The MRI is a non-contrast scan and equipped with monitoring methods that allow conversation with the participants and identification of any anxiety or discomfort. A detailed history for absolute and relative contraindications for a non-contrast MRI will be taken as set out in MRI SOP.

7.9 Expected Adverse Events Associated with Prostate M-P US

Minimal rectal discomfort during the procedure

An antispasmodic agent such as Hyoscine butylbromide should be administered prior to the scan. If there are contra-indication then glucagon maybe used. These are standard injections used during MRI scans. Side effects include blurred vision, dry mouth, dizziness, increased heart rate, constipation and pain at the injection site.

7.10 Expected Adverse Events Associated with Prostate Biopsy

The expected risks of the biopsy procedure include:

- Blood in the urine (Haematuria) is common for up to 48 hours
- Pain passing urine (Dysuria) is common for up to 24 hours
- Blood in the semen is common (Haemospermia) for up to 3-4 months
- Temporary pain/discomfort in the perineal area
- Temporary problems with erections for up to 6-8 weeks (less than 1 in 20, <4-6 weeks)
- Retention of urine requiring a temporary catheter (1 in 100)
- Prostatitis (inflammation or infection of the prostate (1 in 100)
- Infection requiring admission and intravenous antibiotics (0.5-4%)

The majority of biopsies will be performed under local anaesthetic and/or sedation. A small proportion might be offered a general anaesthetic for technical reasons and patient preference as per local standard practice. The expected risks from undergoing the local anaesthetic and conscious sedation procedure include:

- Nausea and vomiting (1 in 10).
- Minor bruises from intravenous catheters (drips) are common.
- Occasionally extensive bruising, temporary hardening of the vein (phlebitis) or infection can occur from intravenous catheters (1 in 20).
- Dizziness/Vertigo

PROSTAGRAM	Protocol no: 18HH4595	Sponsor: Imperial College London	V 1.01MAY2019
-------------------	---------------------------------	---	----------------------

- Confusion/Disorientation
- Respiratory depression and apnoea (rare)
- Anaphylaxis to Local Anaesthetic (1 in 200 000)

There are expected risks associated with the procedure under general anaesthetic including:

- Nausea and vomiting (1 in 10).
- Most men will have a dry cough for an hour or two and may experience a sore throat for 24 hours. This occurs because a mask and /or tube are placed in the throat during the anaesthetic.
- Minor bruises from intravenous catheters (drips) are common.
- Occasionally extensive bruising, temporary hardening of the vein (phlebitis) or infection can occur from intravenous catheters (1 in 20).
- Death. The known risk of death under anaesthesia in the UK is 1 in 150,000 anaesthetics.

7.11 Reporting of SAEs

Rapid reporting of all SAEs i.e. within 24 hours, occurring during the study must be performed as detailed in SAE reporting instructions. If the investigator becomes aware of safety information that appears to be related to the trial, involving a subject who participated in the study, even after an individual subject has completed the study, this should be reported to the Sponsor.

All SAEs will be reviewed by the Chief Investigator or a designated medically qualified representative to confirm expectedness and causality.

Reporting of SAEs and review by the CI will be via the trial data collection system (CRF/eCRF).

7.12 Related SAEs

Related: resulted from administration of any of the research procedures

7.13 Unexpected SAEs

Unexpected: type of event is not listed in the protocol as an expected occurrence

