7.14 Reporting of SAEs that are related and unexpected

An SAE form should be completed and faxed to the Chief Investigator within 24 hours. However, relapse, death and/or hospitalisations for elective treatment of a pre-existing condition do not need reporting as SAEs.

PROSTAGRAM	Protocol no: 18HH4595	Sponsor: Imperial College London	V 1.01MAY2019
-------------------	---------------------------------	---	----------------------

All SAEs should be reported to the relevant REC where in the opinion of the Chief Investigator, the event was:

- 'Related', i.e. resulted from the administration of any of the research procedures; and
 - 'Unexpected', i.e. an event that is not listed in the protocol as an expected occurrence
- Reports of related and unexpected SAEs should be submitted within 15 days of the Chief Investigator becoming aware of the event, using the NRES SAE form for non-IMP studies. The Chief Investigator must also notify the Sponsor of all SAEs. Local investigators should report any SAEs as required by their Local Research Ethics Committee, Sponsor and/or Research & Development Office.

Contact details for reporting SAEs are as follows:

Joint Research Compliance Office

Imperial College London and Imperial College Healthcare NHS Trust

E-mail: [contact]

Chief Investigator

[name] [name]

Imperial College London, Charing Cross Campus

E-mail: [contact]

[contact] (Mon to Fri 09.00 – 17.00)

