8.2 Study Discontinuation by the Chief Investigator

If an unwanted effect is considered severe by the Chief Investigator and endangers the health of all patients, the study will be discontinued after agreement with the Sponsor.

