**Table 1.5. 2: Incidence of expected adverse events (see Appendix 3)**

Event class	Total - n (%)
Expected study-related adverse events:	xx (xx%)
Haematomas and ecchymoses around venepuncture site	xx (xx%)
Minor discomfort	xx (xx%)
Infection	xx (xx%)
Expected adverse events associated with MRI:	xx (xx%)
Claustrophobia	xx (xx%)
Anxiety/Stress	xx (xx%)
Discomfort	xx (xx%)
Expected adverse events associated with Prostate M-P US:	xx (xx%)
Minimal rectal discomfort during the procedure	xx (xx%)
Expected adverse events associated with Prostate Biopsy:	xx (xx%)
	xx (xx%)

Imperial Clinical Trials Unit	STATISTICAL ANALYSIS PLAN	PROSTAGRAM
-------------------------------	---------------------------	------------

Blood in urine (Haematuria)	xx (xx%)
Pain passing urine (Dysuria)	xx (xx%)
Blood in semen (Haematospermia)	xx (xx%)
Temporary pain/discomfort in the perineal area	xx (xx%)
Temporary problems with erections for up to 6-8 weeks	xx (xx%)
Retention of urine requiring a temporary catheter	xx (xx%)
Prostatitis	xx (xx%)
Infection requiring admission and intravenous antibiotics	xx (xx%)
Expected risks from undergoing local anaesthetic:	xx (xx%)
Nausea and vomiting	xx (xx%)
Minor bruises for intravenous catheters	xx (xx%)
Extensive bruising, temporary hardening of vein (phlebitis) or infection	xx (xx%)
Dizziness/Vertigo	xx (xx%)
Confusion/Disorientation	xx (xx%)
Respiratory depression and apnoea	xx (xx%)
Anaphylaxis to local anaesthetic	xx (xx%)
Expected risks from undergoing general anaesthetic:	xx (xx%)
Nausea and vomiting	xx (xx%)
Dry cough	xx (xx%)
Minor bruises from intravenous catheter	xx (xx%)
Extensive bruising, temporary hardening of the vein (phlebitis) or infection	xx (xx%)
Death	xx (xx%)
Other adverse event (specify):	xx (xx%)
...	xx (xx%)
Total	xx (xx%)

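### A related death under general anaesthetic, or a life-threatening form of a listed event, is classed as expected and falls outside the 15-day ethics report

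*Protocol*

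**What the plan says.** Protocol 7.13 gives the definition: "Unexpected: type of event is not listed in the protocol as an expected occurrence". Protocol 7.14, which governs reports to the REC, uses the same test: "Unexpected', i.e. an event that is not listed in the protocol as an expected occurrence". It then sets the deadline: "Reports of related and unexpected SAEs should be submitted within 15 days of the Chief Investigator becoming aware of the event".

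Protocol 7.10 supplies the list for biopsy. Among the biopsy risks is "Infection requiring admission and intravenous antibiotics (0.5-4" (per cent). Among the local anaesthetic and sedation risks are respiratory depression and apnoea, given as rare, and "Anaphylaxis to Local Anaesthetic (1 in 200 000". Among the general anaesthetic risks is "Death. The known risk of death under anaesthesia in the UK is 1 in 150,000 anaesthetics". SAP Appendix 3 (20.3.4) repeats the list. SAP Table 1.5.2 tabulates death as an expected adverse event under the heading "Expected risks from undergoing general anaesthetic".

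Other reporting routes do not depend on expectedness. All SAEs are reported within 24 hours and reviewed by the Chief Investigator or a medically qualified delegate (7.11). The sponsor is told of all SAEs (7.14). The annual report to the REC details them all (7.15). Urgent safety measures, if taken, are notified to the REC within three days (7.16).

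**The concern.** The rule asks whether the kind of event appears on the list. It does not ask how severe the event was or how it ended. The list mixes two things: the risks one would explain to a man before a biopsy, and the reference set used to decide what the REC must hear about quickly. A very rare catastrophe belongs in the first and does not fit the second. With death on the list, a man who dies under anaesthesia for a study biopsy has had a related but expected SAE, and the plan as written asks for no 15-day report.

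What is at stake is prompt review by a body outside the study team and sponsor. The participants are men from the community at average risk, and some will be biopsied only because a study test was positive.

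**Working it through.** **Classification.** There is no planned figure to reproduce for the rule itself, so the sections are set side by side. The SAE criteria are in 7.6.1.

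| Event, judged related | On the 7.10 list? | Class under 7.13 and 7.14 | 15-day REC report |
|---|---|---|---|
| Death under general anaesthetic for a biopsy | Yes, by name | Expected | Not required |
| Life-threatening anaphylaxis to local anaesthetic | Yes | Expected | Not required |
| Life-threatening respiratory depression or apnoea | Yes | Expected | Not required |
| Life-threatening infection after admission | Yes, as infection requiring admission | Expected by type | Not required |
| Fatal sepsis after a local anaesthetic biopsy | Infection admission is listed; death is listed only for general anaesthetic | Not settled | Not settled |

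**Planning figures (Protocol 9.1).** MRI-positive men with normal PSA: 13.37% × 89.6% = 11.98%, or 59.75% × 89.6% = 53.54%. MRI-positive men with raised PSA: 73% × 10.4% = 7.59%. The sums are 19.57% and 61.13%, which match the protocol's 19.6% and 61.1%.

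**Men biopsied.** Under 6.6 every man with a raised PSA also goes to biopsy, so the share positive on MRI or PSA is:

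- low: 11.98 + 10.4 = 22.38%
- high: 53.54 + 10.4 = 63.94%

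For 366 men this gives 82 to 234 biopsies, and for 406 men 91 to 260. The full range is 82 to 260. It assumes that every positive man accepts biopsy, and it leaves out men positive on ultrasound only, for whom the documents give no rate.

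**Events at the 7.10 rates** (count = men × rate; chance of at least one = 1 − (1 − rate)^men).

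- Infection admissions: 82 × 0.005 = 0.41 up to 260 × 0.04 = 10.4. The chance of at least one is 1 − 0.995^82 = 34% at the low end and 1 − 0.96^260, above 99.9%, at the high end.
- Anaesthetic deaths, if all 260 men had a general anaesthetic: 260 / 150,000 = 0.0017. This is an upper bound, because 7.10 expects general anaesthetic in only a small proportion.
- Anaphylaxis, if all 260 had local anaesthetic: 260 / 200,000 = 0.0013.

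Some infection admissions are therefore likely on most of this range, and 7.10 reasonably foresees them. Death and anaphylaxis are not events anyone would anticipate in a study of this size, yet they carry the same label.

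**The case against.** The strongest reply is that the list is narrower, and the reviewer freer, than a literal reading allows. Death appears only under general anaesthetic; most biopsies use local anaesthetic and/or sedation. Several entries carry their own limits: haematuria is given a duration, erectile problems are called temporary, and prostatitis is separate from infection needing admission. An event type can therefore include severity, and a clinician need not class haematuria leading to admission as the listed haematuria. Section 7.11 has a medically qualified person confirm expectedness, and 7.14 applies the REC rule in the Chief Investigator's opinion. Every SAE reaches the sponsor, local investigators report as their own bodies require, and the Trial Management Group can refer matters to the Trial Steering Committee (12.2).

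Much of this stands. A reader might infer that any procedure-related death is expected; the documents do not support that, since the death entry belongs to one anaesthetic route. A reader might also infer that such events escape oversight; they do not. And a single death exceeding its expected count several hundred-fold says little, because that holds for any very rare event.

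What does not fall away is the general anaesthetic death, which is on the list by name, and the life-threatening listed event. Discretion exists, but listing is the only criterion the protocol gives for exercising it. The other routes do not replace the 15-day report: the annual report may come much later, and the three-day notice applies only once urgent measures have been taken.

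**Conclusion.** The point holds as a defect in a reporting definition. Read as written, 7.13 and 7.14 keep a related general anaesthetic death, and life-threatening forms of listed events, out of the 15-day REC report, and leave a fatal outcome of a listed event under local anaesthetic undecided. The number of affected events is probably small, but the death and life-threatening cases are those for which prompt review matters most. The change is worth making, and no planned figure or analysis is affected.

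This rests on a literal reading of the two definitions. The SAE reporting instructions (7.11) and the Trial Steering Committee charter (12.1) are separate documents and may add detail. The counts rest on the planning prevalences and biopsy assumptions shown above.

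Two further inferences should be resisted:

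- **An excess over the 7.10 rates should itself trigger a report.** With no minimum denominator this would misfire. One infection admission in the first 24 biopsies is 1/24 = 4.2%, above the quoted range, and the chance of at least one by then is 11% at a true rate of 0.5% and 62% at 4%. Retention is listed at 1 in 100, so one case in the first 99 biopsies exceeds it; at exactly 1% the chance of that is 1 − 0.99^99 = 63%.
- **Section 8.2 can never apply to biopsy harm**, because its condition reads "If an unwanted effect is considered severe by the Chief Investigator and endangers the health of all patients" and not all men are biopsied. That section concerns stopping the study, not classifying events, and any enrolled man may screen positive. It is a separate matter.

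**What to change.** 1. In both 7.13 and 7.14, define an SAE as unexpected if its nature, severity or outcome is not consistent with the 7.10 entry. Changing only 7.13 would leave the old test in the section that governs REC reports.
2. In both sections, state that a fatal or life-threatening outcome related to a study procedure is reported to the REC within 15 days whether or not its type is listed. This also settles the local anaesthetic case.
3. Move death from the expected-event lists in Protocol 7.10, SAP Table 1.5.2 and SAP Appendix 3 to risk information.
4. Set no frequency trigger. Instead, give the combined steering and monitoring committee (SAP section 17) cumulative biopsy-related SAE counts, with the number of men biopsied, beside the 7.10 rates at its meetings.

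Section 7.14 also has a sentence excusing some events from SAE reporting that can be read as covering death. It is a separate point, but should be reconciled at the same time so that it does not contradict step 2.

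The cost is rewording in those places and an occasional extra REC report. At the quoted rates, deaths and anaphylaxis would add almost none. Any extra reports would come mainly from life-threatening infections, a subset of the 0.4 to 10.4 admissions whose size the documents do not give.
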